The model-recommended MTD is the dose that satisfies the following 3 conditions:

- 1) The empirical posterior probability that the "DLT rate of 16% to < 33%" is greater than a prespecified value (ie, 50%);
- This probability needs to be the largest among the dose levels that satisfy the EWOC condition (ie, the probability that the "DLT rate > 33%" must be less than 30%);
- 3) The minimum number of participants (ie, 6 participants) was treated at this dose level.

The final recommended MTD/RP2D will be based on the recommendation from the BLRM/BLRM-Copula and the overall assessment of all available safety, PK/PD, and efficacy data. Lower doses of BMS-986226 may be tested if none of the planned doses are found to be tolerable as monotherapy or in combination with either nivolumab or ipilimumab. Such decisions will be made after discussion and agreement between the investigators and the BMS Medical Monitor/Study Director (or designee).

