1.2 Prior Specification for BMS-986226 Monotherapy

The Bayesian approach requires the specification of prior distributions for model parameters, which include parameters (α_1 , β_1) for BMS-986226. The prior distributions for BMS-986226 single agent activity were derived using a weakly informative prior, as well as discussion with the Bristol-Myers Squibb (BMS) clinical team. Details are provided below.

Weakly Informative Prior

- The median DLT rate at the reference dose (BMS-986226 at 800 mg every 4 weeks) was assumed to be 30%, that is, mean $(\log(\alpha_1)) = \text{logit}(0.3) = \log(0.3/(1-0.3)) = -0.847$.
- A doubling in dose was assumed to double the odds of DLT, that is, mean $(\log(\beta_1)) = 0$.

The standard deviation (sd) of $log(\alpha_1)$ was set to 1.53 using the following steps:

- If the toxicity probability range was set to be [1%, 99%], then the toxicity interval would be logit (0.99)-logit (0.01) = 9.19.
- To cover 99.7% of the variance, the toxicity interval will cover $6 \times sd (\log(\alpha_1))$, which gives us $sd (\log(\alpha_1)) = 9.19/6 = 1.53$.

Correspondingly, the standard deviation of $log(\beta_1)$ was set to 1, which allows for considerably larger prior uncertainty for the dose toxicity.

- 1) The correlation between $\log(\alpha_1)$ and $\log(\beta_1)$ was set to 0.
- 2) $Log(\alpha_1)$ and $log(\beta_1)$ follow a bivariate normal distribution.

Through those steps, the prior obtained is given in Table 1.2-1.

Table 1.2-1:Prior Distribution for Model Parameters for BMS-986226

Parameter	Means	Standard Deviations	Correlation
$\log(\alpha_1), \log(\beta_1)$	(-0.847, 0)	(1.53, 1)	0

This prior will be fitted into EAST[®] v6.3.1 Dose Escalation Module by Cytel for the Monotherapy Escalation of BMS-986226 as stated in model setup section.

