2 DECISION RULE FOR DOSE ESCALATION AND SIMULATION

Dose escalation recommendations for BMS-986226 monotherapy will be based on the inference from the Bayesian posterior and the probability that the true DLT rate for each dose lies in 1 of the following categories:

- [0%, 16%) under-dosing
- [16%, 33%) targeted toxicity
- [33%, 100%] excessive toxicity

Note: "[" or "]" is inclusive of the respective endpoint, and "(" or ")" exclusive of the respective endpoint.

These boundaries are similar to the toxicity boundaries used by a rule-based design (ie, 3 + 3 design) in that a minimum is set at 16% (~ 1 in 6) DLT rate and a maximum at 33% (~ 2 in 6) DLT rate. Following the principle of EWOC, dose recommendations for the next cohort will be based on the Bayesian model after DLT information becomes available during the DLT period, accounting for all of the available data from the administered doses, and the candidate doses are the ones fulfilling the overdose criterion that there is less than 30% chance of excessive toxicity. Only the candidate doses will be considered for the next cohort. While the Bayesian model will use DLT information from the DLT period only, clinical assessment will take into consideration of the totality of available data including pharmacokinetics (PK)/pharmacodynamics from all treated participants.

Stopping Rules:

The following is the general stopping rules of BLRM (-Copula) during Dose Escalation:

• If all of 30 DLT evaluable participants are treated.

- If all of the current pre-specified doses are considered intolerable according to the pre-specified cutoff (ie, EWOC criteria), then the model will recommend stopping the current dose level and a new dose level lower than the current lowest dose level will need to be identified.
- The maximum number of DLT-evaluable participants in a dose level will be 12. This limit is set to avoid instances in which the model could recommend adding subjects indefinitely to a specific dose level due to uncertainty in the tolerability profile.
- If, for a specific dose level, 6 subjects have been treated and the chance of determining that the dose level to be the "target" dose is > 50%, then the model will suggest to stop and declare the current dose level to be the maximum tolerated dose (MTD).

Model-recommended MTD:

The MTD is the dose that satisfies the following 3 conditions:

- 1) The empirical posterior probability that the 'DLT rate of 16% -< 33%' is greater than 50%.

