2.1 Simulation Parameters

One thousand trial simulations will be used for each scenario. All simulations will be run using EAST v6.3.1 software for BLRM model for the BMS-986226 monotherapy. The number of subjects to be treated in each cohort in a specific dose level and the stopping rules used to declare MTD are defined as:

- Fixed cohort size: 3
- Probability of overdosing: < 30%
- Probability of achieving the target toxicity: > 50%
- Maximum number of participants treated: 30
- Minimum number of participants treated at a given dose level in order to declare MTD: 6
- Maximum number of participants at a dose:12

The provisional dose levels for BMS-986226 monotherapy are 25 mg, 80 mg, 200 mg, 400 mg, and 800 mg.

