% DLT, true DLT rate; % MTD, proportion of the dose selected as the MTD; # Pts, average number of participants by assuming 3 participants for skipped dose level where the true toxicity rate is below the target rate; # DLTs, average number of DLTs by assuming no DLT for skipped dose level where the true toxicity rate is below the target rate; Fitted MTD: fitted MTD at 30% as the target toxicity rate; % toxicity observed, average proportion of DLTs given the doses were tried

The average sample size in this simulation was observed to be no more than 20 participants. The results for the scenarios of narrow safety window and all high show how the EWOC principle limits the risk of exposing participants from a toxic dose level. Overall, the scenarios illustrated above demonstrate that the model performs well in the hypothetical scenarios investigated.

3 INTERIM MONITORING CASE STUDY TO ILLUSTRATE PROVISION OF DOSE RECOMMENDATIONS DURING DOSE-ESCALATION

In order to provide a comprehensive view of the dynamics of the models, different hypothetical scenarios exploring all possibilities are examined. For the simplicity of illustration purposes, a static cohort size of 3 subjects is applied for dose levels 25 mg, 80 mg, 200 mg, 400 mg, and 800 mg in the BMS-986226 monotherapy. This cohort size could vary during the actual clinical trial, and the BLRM models are designed to fit various different cohort sizes, adaptively. In general, there are 4 possible scenarios for a specific dose level, which are 0 DLT observed in 3 total subjects in that cohort (denoted as 0/3), 1 DLT observed in 3 subjects (1/3), 2 DLTs observed in 3 subjects (2/3), and 3 DLTs observed in 3 subjects (3/3).

During interim monitoring, posterior probabilities will be updated when there is new DLT information available. The following three visualization plots will be produced to reflect the real time dose-DLT relationship, to quantify benefit (in the form of target dosing) and risk (in the form of overdosing and underdosing) during model's recommendation process, and to facilitate clinical team's interpretation of the model recommendations for the final decision making:

- Dose-DLT profile for the doses ranging between 0 mg and 800 mg (Figure 3-1).
- Stacking histograms displaying predictive probabilities on DLT rates classified into 3 different categories (Underdosing, Target dosing, and Overdosing) (Figure 3-2).

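### Table 2.2.1-1's MTD columns do not follow the protocol's three-condition MTD rule: under it no dose qualifies in roughly 20-59% of simulated trials in scenarios 1-4, against 0-6.6% printed

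*Combined protocol and SAP*

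**What the plan says.** The model-recommended MTD is defined twice, in protocol Section 10.1.1 and in Appendix 10 Section 2, and the conditions are joint. The first, in Appendix 10, reads "The empirical posterior probability that the 'DLT rate of 16% -< 33%' is greater than 50"%; Section 10.1.1 says the same probability "is greater than a prespecified value (ie, 50"%). The second requires that probability to be the largest among doses meeting the EWOC limit (less than 30% probability of excessive toxicity). The third requires at least 6 participants at the dose.

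Appendix 10 Section 2.1 lists the settings for declaring the MTD in the simulation, and these include "Probability of achieving the target toxicity: > 50"%. The stopping rules in Appendix 10 Section 2 also cap a dose level at 12 DLT-evaluable participants and the escalation at 30. The 12-participant cap is explained as a guard against adding people to one level without end. Nothing says that reaching a cap makes that dose the MTD.

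Table 2.2.1-1 (Appendix 10 Section 2.2.1) defines its selection row as "MTD, proportion of the dose selected as the MTD" and has a separate column for trials with no MTD selected: 0 (by prior), 6.6 (flatter), 1 (narrow window), 0.2 (all low) and 85% (all high). The text below it concludes that the scenarios "demonstrate that the model performs well in the hypothetical scenarios investigated".

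**The concern.** With at most 12 participants at a dose, a posterior probability above 50% for a 17-point-wide interval is demanding. A table in which almost every trial in scenarios 1-4 clears that bar is surprising.

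These are the only operating characteristics given for Part A, and the performance claim rests on them. If the columns count something other than what the protocol calls the MTD, a reader cannot tell how often the written rule would yield an MTD. The gap is widest where toxicity is low. The team would also have no stated model output for a common end state: the cap reached with a target probability of 50% or less.

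**Working it through.** **Inputs (Appendix 10).**
- Model: logit(p) = log(α) + β·log(dose/800).
- Prior centre: "The median DLT rate at the reference dose (BMS-986226 at 800 mg every 4 weeks) was assumed to be 30"%, so mean log(α) = log(0.3/0.7) = −0.847. Its SD "was set to 1.53 using the following steps".
- Slope: "A doubling in dose was assumed to double the odds of DLT", so mean log(β) = 0, with SD 1 and correlation 0.
- Doses 25, 80, 200, 400 and 800 mg, starting at 25 mg, cohorts of 3, skipping allowed as in Section 2.2.1.
- Next dose: the EWOC-eligible dose with the largest target probability.
- Stop when the recommended dose has at least 6 treated and target probability above 50%, or already has 12, or 30 are treated in total, or no dose is eligible.
- True DLT rates from the table. The narrow-window row is out of order in the text available, so I read it as 3/7/18/31/80%.

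The posterior was computed by numerical integration on a grid, with 10,000 trials per scenario for the figures below. Two end-of-trial labels were applied to the same trials: (a) the dose recommended at the stop is called the MTD; (b) all three written conditions must hold.

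**Step 1: reproduce the printed rows, label (a)** (% at 25/80/200/400/800 mg; none).

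| Scenario | Printed | Recomputed, label (a) |
|---|---|---|
| By prior | 0/0.9/9.9/61/28.2; 0 | 0/0.7/10.8/59.1/29.4; 0.0 |
| Flatter | 3.9/11.9/22.2/38.5/16.9; 6.6 | 3.0/12.4/23.5/38.5/17.0; 5.6 |
| Narrow window | 0.4/7.9/40.7/49.8/0.2; 1 | 0.2/7.2/44.4/47.7/0; 0.4 |
| All low | 0.1/0.8/5.4/39.2/54.3; 0.2 | 0/0.7/7.2/40.1/52.0; 0.0 |
| All high | 11.6/2.6/0.7/0.1/0; 85 | 7.9/4.3/0.4/0/0; 87.5 |

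Average sample sizes are 19.2, 18.1, 19.1, 19.1 and 7.1, against 18.2, 17.4, 18.3, 18.4 and 7.0 printed.

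**Step 2: apply the written rule, label (b), to the same trials.**

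| Scenario | No MTD, printed | No MTD, written rule | Range over repeat runs |
|---|---|---|---|
| By prior | 0 | 43.3 | 40-44 |
| Flatter | 6.6 | 28.9 | 28-30 |
| Narrow window | 1 | 21.3 | 20-22 |
| All low | 0.2 | 57.2 | 55-59 |
| All high | 85 | 88.2 | 88-89 |

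The difference comes almost entirely from trials that stop at the 12-per-dose cap with target probability at or below 50%: 43.3, 23.0, 20.8 and 57.1% of trials in scenarios 1-4. Label (a) counts these as selections.

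For the doses truly in the target interval in the by-prior scenario (400 and 800 mg), selection falls from 61 + 28.2 = 89.2% printed to 32.8 + 15.9 = 48.7%. In the all-low scenario, selection of 800 mg (true rate 20%) falls from 54.3% to 17.2%.

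**Step 3: a check without simulation.** Take one path: 0/3 at 25 mg, 0/3 at 400 mg, then 12 treated at 800 mg. The posterior target probability at 800 mg for 0 to 5 DLTs is about 0.07, 0.22, 0.44, 0.56, 0.53 and 0.38. With 4 DLTs the overdose probability is 0.37, which fails EWOC. On this path only 3/12 meets all three conditions; 0, 1 or 2 DLTs in 12 cannot make 800 mg the MTD.

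**Step 4: sensitivity of the scenario 1-4 range under label (b).**
- Upper target bound 1/3 instead of 0.33: 19-55%.
- No dose skipping: 19-51%.
- No early stop on target probability: 34-66%.
- Cap closes only that dose and enrolment continues elsewhere up to 30: about 25, 12, 10 and 34%.
- Cap ignored altogether: 7-31%.

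Each variant exceeds the printed figure in each of the four scenarios.

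**The case against.** The strongest reply is that little of consequence changes. The labels are applied after the trial ends, so dose assignment, participants and DLTs per dose, average sample size and overdose control are the same under both. A reader might infer that the model often names no dose. The documents do not support that: under label (a) the model ends with an EWOC-eligible recommendation in about 95% or more of trials in scenarios 1-4 (lowest 100 − 5.6 = 94.4%, flatter). Nor does a missing label block later parts. The final MTD also rests on overall clinical assessment (Section 10.1.1), the Part B and C starting dose depends on a monotherapy dose having cleared the DLT period (Section 5.1), and the Part D and E dose uses all available data (Section 5.1.2.4). All of this stands, and it limits the consequence. It does not rescue a simulation column headed as MTD selection.

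Second, the size depends on how the 12-per-dose cap is read. The document lists it among the stopping rules but words it as a limit for one dose level. If it only closes that level, the figures are roughly halved. That stands as a range, although this reading gives average sample sizes of 22.6 and 23.9 in scenarios 1 and 4, against 18.2 and 18.4 printed.

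Third, my simulation is not the sponsor's software. Average sample size runs up to about 1 participant high, and the Figure 3-2 example gives 0.361 and 0.298 where the protocol prints 0.372 and 0.311. What the software counts as selected is inferred from the match, not documented. Differences of that order cannot explain gaps of 20 points or more.

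Fourth, the appendix describes the all-low scenario as having every dose below target, so naming no MTD there is not plainly poor performance. That is fair, although its 800 mg rate of 20% lies inside 16-33%.

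**Conclusion.** The selection columns of Table 2.2.1-1 and the written MTD rule disagree. Under the three conditions no dose meets the MTD definition in roughly 40-44, 28-30, 20-22 and 55-59% of trials in scenarios 1-4 (printed 0, 6.6, 1 and 0.2%), or about 25, 12, 10 and 34% if the cap closes one dose level only. The all-high scenario shows no material conflict.

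This rests on the stated prior and Section 2.1 settings, on the next-dose rule described with Figure 3-2, and on the reading of the narrow-window rates given above. It is an inconsistency between a rule and a table, not a wrong sum: each printed row adds to 100. A reader might go further and infer that escalation is unsafe or that Part A cannot deliver a dose. Neither follows, because only the MTD label is withheld.

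**What to change.** Reconcile the rule and the table in one of two ways; which rule to adopt is the sponsor's choice.

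1. Keep the three conditions. Re-run the simulation under them, restate the MTD selection row and the not-selected column, and revise the sentence on model performance.
2. If the criterion of more than 50% with at least 6 treated is meant only as an early-stopping trigger, say so in Section 10.1.1 and Appendix 10. Then state what the model reports when a cap ends escalation with target probability at or below 50%, and define the table's selection row to match. The combination rule in Appendix 10 Section 5 already has no 50% condition.

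Under either option, say whether reaching 12 at a dose ends escalation or only closes that level.

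The cost is at most one re-run of an existing simulation and a few sentences. If the rule is kept, the printed figures become less favourable.

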3.1 Example of the BLRM using BMS-986226 Monotherapy Dose Escalation

According to safety consideration and clinical judgement, the dose level 25 mg is recommended as the starting dose for BMS-986226 monotherapy. With the current BMS-986226 prior specified

CA021002

anti-ICOS

in the Section 1.2 and all available DLT information up to 80 mg, a corresponding decision tree illustrating various models' recommendations under all possible scenarios (for dose levels of 200 mg and 400 mg) is provided in Figure 3.1-1.

Tracing a branch of the decision tree in Figure 3.1-1 illustrates the decision making process. Taking the left-most branch of the tree as an example, starting at 25 mg, there were 0 DLT observed at 25 mg in the real clinical trial, the model recommended to escalate to 80 mg (The BLRM actually recommends escalating to dose level 400 mg, but since this is a 16-fold increase of dose and this type of dose skipping is not allowed, the dose level 80 mg is selected), one level above the current treated dose level according escalation rules per protocol. Additionally, if there was 0 DLT observed at 80 mg in real data, the model recommended to escalate further one dose level to 400 mg.

As illustrated in Figure 3.1-1, there are 6 potential decision paths for dose levels 80 mg and moving onwards up to 200 mg. During the actual clinical study, the tree would be narrowed or deepened based on actual DLT. The clinical team will be able to leverage this decision tree to preview decisions at each interim monitoring step and to plan proactively.

Abbreviations: DE = de-escalation; E = escalation; S = stay.

4 BLRM-COPULA MODEL SETUP FOR BMS-986226 AND NIVOLUMAB OR IPILIMUMAB COMBINATION

For Parts B and C of this study, the BLRM-Copula model will be used to evaluate the starting dose and to guide the subsequent doses of BMS-986226 in combination with nivolumab or ipilimumab.

The BLRM-Copula model incorporates the latest information, including monotherapy information from Part A and any available toxicity information in completed portion of Parts B and C, available at the time of dose recommendation. In other words, the model concept covers both the starting doses and any subsequent doses of BMS-986226 in combination with nivolumab or ipilimumab in Parts B and C. Specifically, the starting dose of BMS-986226 in Parts B and C will be guided using the BLRM-Copula model, incorporating available single-agent toxicity profiles of BMS-986226 from the preliminary safety cohorts and Part A and nivolumab or ipilimumab. Any subsequent dose of BMS-986226 in Parts B and C will be evaluated using the BLRM-Copula model, incorporating of BMS-986226, nivolumab or ipilimumab and any available combination toxicity profiles from on-going Parts B and C.

In any case, the dose of BMS-986226 in combination with nivolumab or ipilimumab in Parts B and C will not exceed the maximum administered dose for BMS-986226 monotherapy in Part A. In summary, the doses of BMS-986226 in Parts B and C (combination with nivolumab or ipilimumab) will be determined using all available safety (clinical and laboratory), PK, and target engagement data, and the modelling recommendation using the BLRM-Copula model. The toxicity profiles of both BMS-986226 monotherapy and nivolumab or ipilimumab monotherapy, to be incorporated in the BLRM-Copula model, will be discussed in upcoming subsections. We introduce briefly the technical background of the BLRM-Copula model in the following paragraph.

A copula-type model can be used to cover all general combination cases, including additive and synergistic effects. The combination of the 2 treatments will be explored using a Bayesian hierarchical model by utilizing the toxicity profiles of the single agents as prior marginal profiles for the combination. The following copula-type model⁴ will be used to describe the probability p_{ij} of toxicity when dose level *i* of agent A and dose level *j* of agent B are administered in combination:

$$p_{ij} = 1 - exp(-\left[\left\{-log(1 - p_i^m)\right\}^{1/\gamma_1} + \left\{-log(1 - q_j^n)\right\}^{1/\gamma_1}\right]^{\gamma_1}),$$

where p_i is the prespecified best guess toxicity probability for agent A, q_j is the prespecified best guess toxicity probability for agent B, m and n characterize the individual drug effect, and γ_1 characterizes the drug-drug interactive effect.

The joint toxicity framework models the toxicity rates of both agents as well as their interaction effects in a 7-parameter hierarchical model, where each monotherapy dose-toxicity relationship will be characterized by a 2-parameter BLRM model (see Section 1.1). There are 3 additional parameters for the copula-type model, 1 for each agent (*m* and *n*) as well as 1 for the interaction term (γ_1). A dose-toxicity surface will be characterized for different dose combinations of these 2 agents.

As there are currently no historical data or prior knowledge to indicate how much information is to be borrowed for each of the single agents, parameters m and n are both set to be 1, meaning borrowing 100% of the information from the 2 agents. The above formula is then simplified into a 5-parameter model as follows:

```
Revised Protocol No.: 04
Date: 31-May-2019
```

$$p_{ij} = 1 - exp(-\left[\{-\log(1-p_i)\}^{1/\gamma_1} + \{-\log(1-q_j)\}^{1/\gamma_1}\right]^{\gamma_1}.$$

In each cohort of the study, since only a fixed nivolumab dose (in Part B1) or ipilimumab dose (1 mg/kg in Part B2, 3mg/kg in Part B3) will be used in the combination with BMS-986226, this surface will be simplified into a 2-dimensional dose-toxicity curve. Posteriors for the corresponding 5 parameters (2 logistic regression parameters $[\alpha_1, \beta_1]$ for BMS-986226 and 2 logistic regression parameters $[\alpha_2, \beta_2]$ for nivolumab or ipilimumab, as well as 1 interaction parameter for the copula-type model $[\gamma_1$, which will be discussed in detail in the following section]) will be fitted into the in-house developed model. It implements the above-described theoretical setup.

4.1 Prior Specification for Combination Therapy

In this section, we illustrate the prior specification of parameters in the BLRM-copula model for combination therapies. While we give prior examples for illustration purposes, all of those specifications may be subject to change when new data of monotherapies are available.

